## 3.2 Rationale and risk/benefit assessment

### 3.2.1 Rationale for study design, doses and control groups

This prospective study will employ a randomized, double-blind, placebo controlled design to evaluate the efficacy and safety of esomeprazole for the treatment of GERD in neonatal patients. The primary goal of the pharmacologic treatment of GERD is to reduce the exposure of the esophageal and supraesophageal mucosa to gastric acid by its effect on acid suppression. Currently available therapies for GERD include antacids, histamine-2 receptor antagonists (H2RAs), or proton pump inhibitors (PPIs), and prokinetic agents. Although antacids and the prokinetic agent, cisapride, have been shown to have modest efficacy in infants or children (Cucchiara et al 1984, 1987, Cohen et al 1999), their safety profiles do not support their use as primary therapies in infants (Rudolph et al 2001). In contrast, H2RAs have been considered front-line therapy (Cucchiara et al 2000) and various studies have demonstrated their efficacy in a pediatric population (Rudolph et al 2001).

The dosing of esomeprazole, 0.5 mg/kg, will be based on daily body weight. The rationale of exposure-response relationship was used to extrapolate the esomeprazole dose from adults to children. The esomeprazole exposure (AUC) and the response (efficacy and safety) for pediatric patients was estimated via a comprehensive PK and population PK modeling analysis of the omeprazole PK data in adult and pediatric patients and esomeprazole PK data in adults (Appendix C). The dose of 0.5 mg/kg/day is expected to provide a reasonable chance of efficacy while yielding potential exposures within the safety margin.

At the present time, there is limited safety data for doses of 0.5 mg/kg/day for the very young neonates (less than 5 days). However, data from a recently concluded study (AstraZeneca Clinical Study Report for Study SH-NEC-0001) in infants up to 24 months of age indicate no trends of clinical relevance regarding safety variables in relation to doses of esomeprazole 0.25 mg/kg or 1.0 mg/kg. In addition, preliminary population kinetics data from another study using the same dose of esomeprazole and same target population as Study SH-NEC-0001 do not indicate any safety concerns. For the reasons outlined above, our maximum proposed dose for neonatal studies dealing with pre-term and term neonates with GERD related symptoms will be 0.5 mg/kg/day.

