### **3.3.2 Inclusion criteria**

For inclusion in the study, patients must fulfil all of the following criteria:

1. Patients' parent/guardian must provide written informed consent prior to the execution of any study-related procedures.
2. Patients must be full term or have gestational age  $\geq 28$  to 44 weeks (calculated from last menstruations or ultrasound).
3. Patients must be an inpatient in the Neonatal Intensive Care Unit (NICU), special care nursery, or equivalent hospital ward at the point of study entry and will be expected to remain an inpatient for the treatment period of the study. If the patient is discharged prior to completion of the treatment phase, patients may be given the option of having at home visits for study drug administration at the discretion of the

investigator. These patients will need to be readmitted to the hospital for final study day procedures.

4. Patients must have the following observed clinical findings: any two (either individually or in any combination) of (1) apnea +/- bradycardia +/- oxygen desaturations, (2) vomiting/gagging, (3) irritability/pain at least every second feed or at least twice every eight hours, and present for at least 5 days or increasing in frequency or severity over 3 days. At least 2 of the occurrences of the above should be reproducible during the 8 hour video.
5. Patient's size and medical condition must allow for performance of all study related procedures and administration of investigational product as judged by the investigator.
6. Patients must be on a stable mode of feeding or with minimal variations in feeding as judged by the investigator for at least 2 days prior to randomization.

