### 3.4 CRITERIA FOR DOSE SELECTION FOR ESOMEPRAZOLE PEDIATRIC STUDIES

It has been well established that the inhibition of acid secretion by esomeprazole is well correlated with the exposure (AUC), which is subsequently determined by the (apparent) clearance ( $AUC = \text{Dose}/(CL/F)$ ). The relationship between the esomeprazole exposure (AUC) and the acid inhibition can be adequately described by a sigmoid  $E_{max}$  model

$$\text{Acid inhibition} = (E_{max} \times AUC^\gamma) / (AUC^\gamma + AUC_{50}^\gamma) \quad (3)$$

where  $E_{max}$  is the maximum acid inhibition (100%),  $AUC_{50}$  is a value of AUC achieving 50% acid inhibition and  $\gamma$  is the sigmoidicity factor reflecting the steepness of the exposure and response relationship. The reported value of  $AUC_{50} = 0.68$  umol/L with a sigmoid coefficient  $\gamma = 1.43$  implies that at three times of the  $AUC_{50}$  for this sigmoid  $E_{max}$  exposure and response relationship, the acid inhibition will reach more than 80%. Therefore, we believe a dose that results in AUC 3-fold higher than  $AUC_{50}$  should be considered to be the minimum effective dose in adults.

The 40 mg esomeprazole oral dose has been widely used in the treatment of acid-related disease in adults with no apparent safety concerns. Study SH-QBE-0008 reported that the upper limit of 95% confidence interval of the esomeprazole exposure (AUC) is 16.17 (umol.hr/L) for the 40 mg esomeprazole oral dose in adults, which approximately correspond to 24 times of the AUC50 (0.68 umol.hr/L). Thus, a dose that generates an exposure AUC meeting AUC/AUC50 less than 24 was considered to be a safe dose in adults.

Collectively, an esomeprazole dose with an exposure AUC greater than 3 and less than 24 times of the AUC50 was found to be a reasonable dose for both efficacy and safety in adults. These limits were scaled to different pediatric subject groups according to the difference (if any) in esomeprazole efficacy and safety between adults and pediatric subjects established in 3.1 and 3.2.

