## 4. RESULTS AND DISCUSSIONS:

### 4.1 BRIDGING ESOMEPRAZOLE SAFETY AND EFFICACY BETWEEN ADULTS AND PEDIATRIC SUBJECTS

Proton pump inhibitors (PPI) have shown a remarkable tolerability profile in both adults and children. In an AstraZeneca omeprazole pediatric study (I-250), some children had AUC exposures up to 3 times the mean exposure seen in adults administered the maximum labeled omeprazole dose (40 mg), and no drug related side effects were reported. Examination of literature for the safety of the two proton pump inhibitors with labeling for use in both pediatric subjects and adults, omeprazole and lansoprazole, have not found any significant differences in safety between pediatric subjects and adults at a similar exposure (AUC).

The plot of percent of time with gastric pH>4 and gastric median pH vs. AUC following administration of omeprazole in both adults and pediatric subjects is shown in [Figure 1](#). It indicates that children are no less sensitive to acid inhibition than adults at similar omeprazole exposure. This was also observed in the pediatric study for Lansoprazole, a proton pump inhibitor with a similar mechanism of action to esomeprazole.

These results indicate that it is likely that the difference in safety and efficacy between pediatric subjects and adults at the same omeprazole exposure (AUC) is negligible. These attributes of omeprazole are also likely true for esomeprazole, the S-isomer of omeprazole. Consequently, the dose adjustment for esomeprazole can be based on the differences in esomeprazole pharmacokinetics between pediatric subjects and adults. In addition, the limits of esomeprazole exposure in adults, 3 and 24 times the AUC50 (0.68 umol.hr/L) for lower and upper limits, respectively, can be used for pediatric subjects without adjustment.

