### **4.3 ESOMEPRAZOLE DOSE SELECTION FOR DIFFERENT AGE GROUPS**

#### **4.3.1 NEONATAL PATIENTS, PREMATURE UP TO 1 MONTH CORRECTED AGE**

Esomeprazole will be administered using a nasogastric or orogastric tube and an appropriate esomeprazole solution formulation will be prepared for this age group. Dose in mg/kg will be used for this age group. Doses around 0.5 mg/kg at an increase or a decrease in 0.25 mg/kg

were evaluated. [Table 2](#) shows that 0.25-0.5 mg/kg dose is likely to show a reasonable chance of efficacy and an acceptable safety for body weight ranging from 1 to 6.5 kg. At the present time, there is limited safety data for doses of 0.5 mg/kg/day for the very young neonates (less than 5 days). However, as suggested by the results of other studies (AZ data on file,) and literature reports, there is progressive maturation of the hepatic metabolic enzymes over the first week of life irrespective of gestational age. Therefore, our proposed dose for neonatal studies dealing with pre-term and term neonates with obstructive apnea will be 0.5mg/kg/day during the open label phase. This study population is expected to require at least a 4 day period of investigation prior to enrollment, for other causes of apnea, which may include a full sepsis work up ,EKG, and other various tests indicated per standard medical practice. In addition, both Pneumographic and pH probes studies require an additional day prior to dosing. Therefore, we don't anticipate patients being dosed at an age younger than 5 days.

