17. Lacroix, D. et al, Expression of CYP3A in the human liver—evidence that the shift between CYP3A7 and CYP 3A4 occurs immediately after birth. *Eur J Biochem*, 247(2): 625-34, 1997
18. Anderson, B.J. et al, Scaling for size: some implication for paediatric anaesthesia dosing, *Paediatric Anaesthesia*, 12: 205-219, 2002
19. West, G.B. et al, A general model for the origin of allometric scaling laws in biology. *Science*, 276:122-6, 1997
20. “The pink sheet”, June 17, 2002, p3

**Figure 1. Difference of exposure (AUC) and PD endpoint (percent of time with gastric pH>4, Gastric median Ph) between adults and children with age ranging from 4.5 to 27 months. Square: Children, Circle:Adults**

Table 1 Description of Data Sets Used in the Analysis

Data set	Description	Studies	No. of Subjects						
			0-3 Months	3-12 months	1-11 years	12-16 years	Adults	All	
1	PK/PD studies in repeated iv infusion of Prilosec. PD endpoints: Percent of time with gastric pH>4, Gastric median pH	SH-QBE-0061, Faure, C. et al †	N	--	3	6	--	16	25
			Dose	0.4-1.3 mg/kg iv infusion in 60 minutes				40 mg iv infusion in 30 minutes	--
			Geomean clearance (L/hr)	0.4	3.2	4.8	--	9.7	--
2	PK studies in repeated iv infusion of Prilosec	SH-QBE-0061; Andersson T. et al † , Faure, C. et al †	N	3*	5	8	--	16	32
			Dose	0.4-1.3 mg/kg iv infusion in 30 or 60 minutes				40 mg iv infusion in 30 minutes	--
			Dose ratio relative to adults	1/25	1/3	1/2	--	1	--
3	PK studies in repeated oral dose administration of Prilosec	Prilosec 245, 250, 678 and SH-QBE-0008	Geomean clearance (L/hr)	1.3	1.2	16.6	21.6	24.6	--
			N	3 (1)**	1	37 (24)	25(15)	36 (36)***	102(67)
			Dose	1 mg/kg				0.7/1.4 mg/kg, 10/20 m	20 mg
4	PK studies in repeated oral dose administration of Nexium	SH-QBE-0008	0	1/18	1/20	2/3	1	1	--
			Geomean of clearance (L/hr)	--	--	--	--	13.7	--
			N	--	--	--	--	36 (35)***	36 (35)
			Dose	--	--	--	--	20 mg	--

\* 3 subjects were 10 days old

\*\* Number in the parenthesis is the actual number for the calculation of the geometric mean clearance

\*\*\* Same adult subjects in study SH-QBE-0008

**Table 2 Estimated exposure (AUC/AUC50) for 0-1 month neonates (A value between 3 and 24 indicates a reasonable chance of efficacy and acceptable safety)**

Study	Weight range	Pounds kg	Age: 5 days		Age: 10 days		Age: 15 days		Age: 20 days		Age: 25 days		Age: 30 days	
			2.2	14.3	2.2	14.3	2.2	14.3	2.2	14.3	2.2	14.3	2.2	14.3
			1	6.5	1	6.5	1	6.5	1	6.5	1	6.5	1	6.5

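### Section 3.2.1 places 0.5 mg/kg/day within the safety margin with no age qualifier, yet Appendix C Table 2 flags that dose at 5 days of age, and the entry criteria do not clearly exclude that age

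*Protocol*

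**What the plan says.** Section 3.2.1 of the protocol bases the dose on the modelling in Appendix C and concludes: "The dose of 0.5 mg/kg/day is expected to provide a reasonable chance of efficacy while yielding potential exposures within the safety margin". It adds that safety data are limited below 5 days of age. It does not mention any modelled excess at 5 days or later, and it gives no weight range.

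Appendix C contains the rest:

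- **The limit.** Section 3.4 says that a dose giving AUC/AUC50 "less than 24 was considered to be a safe dose in adults". Section 4.1 says that the limits of 3 and 24 "can be used for pediatric subjects without adjustment".
- **The reading rule.** The title of Table 2 says: "A value between 3 and 24 indicates a reasonable chance of efficacy and acceptable safety".
- **The table.** The 0.50 mg/kg row at 5 days reads 27# at 1 kg and 43# at 6.5 kg, where # marks a potential safety concern. From 10 days on, every value in that row is 23 or lower and unflagged.
- **The text on the table.** Section 4.3.1 says that a 0.25-0.5 mg/kg "dose is likely to show a reasonable chance of efficacy and an acceptable safety for body weight ranging from 1 to 6.5 kg".
- **The age expectation.** The same section says that the authors do not "anticipate patients being dosed at an age younger than 5 days".

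On entry (section 3.3.2), criterion 2 is written in gestational age. Criterion 4 asks for signs "present for at least 5 days or increasing in frequency or severity over 3 days". No inclusion or exclusion criterion states a minimum age since birth.

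**The concern.** The margin statement and the table it rests on disagree for the youngest infants. The limit, the flag and the reassurance all come from the same appendix, so the conflict is internal and needs no outside source.

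Age since birth is what matters here, because the clearance model in Appendix C uses time after birth. A criterion written in gestational age does not control it. The expectation about dosing before 5 days does not fill the gap. It was written for the apnea study D9614C00095, where it rests on a four-day apnea work-up plus a day of pneumographic and pH-probe studies. It is an expectation and not a criterion, and it would not exclude day 5, which is the flagged age.

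The risk-benefit section (3.2.2) only refers back to 3.2.1, so ethics committees and investigators read the margin statement as the protocol's position on exposure. The trial measures no pharmacokinetics (section 4.5) and has no data monitoring board (section 6.7), so an exposure above the limit would not be measured within the study.

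**Working it through.** **Inputs.** All are from Appendix C unless noted.

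- Apparent clearance at 70 kg: 13.6 L/hr; maturation rate: 10.9 per year (equation (6)).
- AUC50: 0.68 umol.hr/L. Upper limit: 16.17/0.68 = 23.8, taken as 24 (section 3.4).
- Dose: 0.5 mg/kg (protocol section 3.4.2).
- Molar mass: not given in the documents. I assume 345.4 g/mol and show 330 to 367.4 as a range.

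**Formula.** CL/F = 13.6 × (WT/70)^0.75 × (1 − exp(−10.9 × age in years)). Ratio = (dose in mg × 1000 / molar mass) / (CL/F) / 0.68.

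**Reproducing Table 2 at 5 days.**

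- Age term: 1 − exp(−10.9 × 5/365.25) = 0.1386.
- 1 kg: CL/F = 13.6 × 0.0413 × 0.1386 = 0.0779 L/hr. Dose = 500/345.4 = 1.448 umol. AUC = 18.6. Ratio = 27.3 (printed 27#).
- 6.5 kg: CL/F = 13.6 × 0.1682 × 0.1386 = 0.317 L/hr. Dose = 3250/345.4 = 9.41 umol. AUC = 29.7. Ratio = 43.6 (printed 43#).
- At 10 days the formula gives 14.7 and 23.4 (printed 15 and 23).

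The other cells agree to within about 0.7 of the printed value, with one exception. The 1.0 mg/kg, 1 kg, 5-day cell prints 24# but computes to 54.7. That cell has no bearing on the 0.50 mg/kg row.

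**Sensitivity to molar mass.** At 5 days, over 330 to 367.4 g/mol, the ratio is 28.6 to 25.7 at 1 kg and 45.7 to 41.0 at 6.5 kg. All values exceed 24.

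**When the model reaches 24** (0.5 mg/kg, 345.4 g/mol):

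| Weight | Day 5 | Day 6 | Day 7 | Day 8 | Reaches 24 at about |
|---|---|---|---|---|---|
| 1 kg | 27.3 | 23.1 | 20.1 | 17.8 | day 5.8 |
| 2 kg | 32.5 | 27.5 | 23.9 | 21.2 | day 7.0 |
| 3 kg | 36.0 | 30.4 | 26.4 | 23.5 | day 7.8 |

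With 367.4 g/mol the crossings are at about days 5.4, 6.5 and 7.3; with a smaller molar mass they come later.

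**Earliest age at first dose under the entry rules.** Suppose signs begin at birth. Before the first dose the plan requires a 24-hour chart on the day before monitoring, 18-24 hours of pH/impedance recording (section 3.1.1) and a site review of the video before randomization (section 3.1.6). The first dose is given on the randomization day (section 3.1.2).

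- Five-day branch of criterion 4: first dose at about day 6 to 7.
- Three-day branch: about day 5, or day 4 if the work-up overlaps the symptom period.

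The implied floor is about 4 to 7 days. On day 7 a 3 kg infant is still above the limit (26.4); on day 5 all three weights are.

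**The case against.** The strongest case on the other side has four parts.

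1. *The limit is not a toxicity threshold.* It is the upper 95% limit of adult exposure on 40 mg, and # marks only a potential concern. A reader might infer that the dose is shown to be unsafe. The documents do not support that: Table 2 holds modelled means, and section 3.2.1 also cites infants given up to 1.0 mg/kg, and children with omeprazole exposures up to three times the adult mean, without safety signals. This stands against any claim of harm. It does not make the exposure fall within the margin that Appendix C defined.

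2. *The excess is brief.* At constant weight, an infant first dosed on day 5 exceeds 24 for one daily dose at 1 kg, two at 2 kg and three at 3 kg, out of 14. This stands and limits the size of the point.

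3. *There is an age floor in practice.* A reader might infer that infants can be dosed from birth. They cannot: criterion 4 and the baseline procedures take several days. But the resulting floor of about 4 to 7 days overlaps the flagged range.

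4. *The 6.5 kg column is unrealistic so early in life.* It would be tempting to quote its excess of 82% at day 5 (43.6/24 = 1.82) or its crossing near day 9.7. That weight is unlikely at that age, so neither figure should carry the argument. The 1 kg column is flagged as well.

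Sections 3.2.1 and 4.3.1 also disclose limited data below 5 days, and section 4.3.4 of Appendix C calls the doses open to revision. Neither tells the reader that Table 2 flags this dose at 5 days.

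**Conclusion.** The point holds as an internal contradiction. The unqualified statement in section 3.2.1, and the acceptance of 0.25-0.5 mg/kg for 1 to 6.5 kg in Appendix C section 4.3.1, conflict with Table 2 at 5 days. At that age the modelled ratio exceeds 24 by 14% at 1 kg (27.3/24), 35% at 2 kg (32.5/24) and 50% at 3 kg (36.0/24). The excess ends between about day 5.8 and day 7.8 for those weights. The entry criteria leave part of that window open.

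The flag itself is printed and needs no assumption. The day-by-day figures rest on equation (6), on a molar mass that is assumed, and on population means. They also extrapolate: the youngest infants behind the age term were 10 days old (Appendix C Table 1, footnote), so the true exposure at day 5 could lie on either side of the modelled value. The conclusion is that a safety statement is wrong as written for the youngest eligible infants. It is not that the dose is harmful or that another dose or age rule is right.

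**What to change.** The sponsor should reconcile four places so that the safety-margin statement and the eligible postnatal ages agree: section 3.2.1, Appendix C section 4.3.1, Appendix C Table 2 and the entry criteria in sections 3.3.2 and 3.3.3. How to resolve the conflict is a clinical decision for the sponsor.

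Until that is done, section 3.2.1 should disclose that Table 2 flags this dose at 5 days of age, and that the expectation about dosing age in Appendix C was written for the apnea study. The 1.0 mg/kg, 1 kg, 5-day cell of Table 2 should be checked in the same pass.

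The cost is a few sentences of protocol text, plus an amendment under section 7.4 if the resolution changes the entry criteria. No new data collection is needed: date of birth and each administration of study drug are already recorded (sections 4.2 and 3.7).

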### **3.2.2 Risk/benefit and ethical assessment**

See Section 3.2.1 for rationale for a placebo-controlled study design.

## **3.3 Selection of study population**

### **3.3.1 Study selection record**

Investigator(s) must keep a record of patients who were considered for enrollment but were never enrolled eg, patient screening log. This information is necessary to establish that the patient population was selected without bias.

### **3.3.2 Inclusion criteria**

For inclusion in the study, patients must fulfil all of the following criteria:

1. Patients' parent/guardian must provide written informed consent prior to the execution of any study-related procedures.
2. Patients must be full term or have gestational age  $\geq 28$  to 44 weeks (calculated from last menstruations or ultrasound).
3. Patients must be an inpatient in the Neonatal Intensive Care Unit (NICU), special care nursery, or equivalent hospital ward at the point of study entry and will be expected to remain an inpatient for the treatment period of the study. If the patient is discharged prior to completion of the treatment phase, patients may be given the option of having at home visits for study drug administration at the discretion of the

investigator. These patients will need to be readmitted to the hospital for final study day procedures.

4. Patients must have the following observed clinical findings: any two (either individually or in any combination) of (1) apnea +/- bradycardia +/- oxygen desaturations, (2) vomiting/gagging, (3) irritability/pain at least every second feed or at least twice every eight hours, and present for at least 5 days or increasing in frequency or severity over 3 days. At least 2 of the occurrences of the above should be reproducible during the 8 hour video.
5. Patient's size and medical condition must allow for performance of all study related procedures and administration of investigational product as judged by the investigator.
6. Patients must be on a stable mode of feeding or with minimal variations in feeding as judged by the investigator for at least 2 days prior to randomization.

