## PROTOCOL SYNOPSIS

---

**A randomized, double-blind, placebo-controlled study to evaluate the efficacy and safety of esomeprazole once daily for the treatment of gastroesophageal reflux disease (GERD) in neonatal patients, including premature and up to 1 month corrected age**

---

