### **Target patient population**

Male and female neonatal patients, including premature and up to 1 month corrected age, with symptoms of GERD (gestational age  $\geq 28$  to 44 weeks, calculated from last menstrual period or by ultrasound) admitted to a Neonatal Intensive Care Unit (NICU), special care nursery or equivalent hospital ward.

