## LIST OF ABBREVIATIONS AND DEFINITION OF TERMS

The following abbreviations and special terms are used in this study protocol.

Abbreviation or special term	Explanation
Acidic Reflux Episode	Retrograde bolus movement of gastric acid into the esophagus as defined by a pH/impedance measurement with a pH drop < 4
AE	Adverse event (see definition in Section 4.7.1.1)
ANCOVA	Analysis of covariance
Assessment	An observation made on a variable involving a subjective judgement
AUC	Area under the curve
AZDD	AstraZeneca Drug Dictionary
BP	Blood Pressure
°C	Degrees Celsius
CRF	Case Report Form
CSA	Clinical Study Agreement
DCF	Data Clarification Form
eCRF	Electronic Case Report Form
ECG	Electrocardiogram
Ethics Committee	Synonymous to Institutional Review Board and Independent Ethics Committee
EU	European Union
GER	Gastroesophageal Reflux
GERD	Gastroesophageal Reflux Disease
GCP	Good Clinical Practice
GMP	Good Manufacturing Practice
ICH	International Conference on Harmonisation
I-GERQ	Infant Gastroesophageal Reflux Questionnaire
International Co-ordinating investigator	If a study is conducted in several countries the International Co-ordinating Investigator is the Investigator co-ordinating the investigators and/or activities internationally.
IRB	Institutional Review Board
ITT	Intent-to-treat
kg	Kilogram

Abbreviation or special term	Explanation
Measurement	An observation made on a variable using a measurement device.
MedDRA	Medical Dictionary for Regulatory Activities
Medical History	Any clinical observation obtained or reported by a patient or caretaker regarding past, present or newly developed signs or symptoms. This applies to both baseline and/or follow up collection of clinical information.
mg	Milligram
mL	Milliliter
NCR	No Carbon Required
Neonatal patients	Infants who are born full term or premature (up to one month corrected age)
NICU	Neonatal Intensive Care Unit
OAE	Other Significant Adverse Event (ie, adverse events of particular clinical importance, other than SAEs and those AEs leading to discontinuation of the patient from study treatment; see definition in Section 4.7.1.1).
Outcome variable	A variable (usually a derived variable) specifically defined to be used in the analysis of a study objective.
Parameter	A quantity (usually unknown) that characterizes the distribution of a variable in a population of patients.
PK	Pharmacokinetic
PP	Per-protocol
PPI	Proton Pump Inhibitor

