## Abstract

The esomeprazole doses selected for the pediatric GERD studies were based on the methodologies described in this document. These doses will provide a reasonable chance of efficacy with a supportable safety margin. The doses selected for each age group are outlined below:

AZ Protocol #	Age Group	Design	Dose(s)
D9614C00095	Premies 0 up to 1 month, corrected age	A Multi-Center, Randomized, Double-Blind, Placebo-Controlled, Parallel Group, Treatment-Withdrawal Study to Evaluate the Pharmacokinetics, Efficacy, and Safety of Esomeprazole for the Treatment of Gastroesophageal Reflux (GER)-Associated Apnea in Neonatal Patients, Premature up to 1 Month Corrected Age  Open-label phase =5 to 7 days  Randomized withdrawal phase =up to 1 week	0.25-0.5 mg/kg  Open-label phase: 0.5 mg/kg  Randomized withdrawal phase: 0.5 mg/kg, 0.25 mg/kg or placebo
D9614C00096	Infants 1 month up to 11 months, inclusive	A Multicenter, Randomized, Double-Blind, Placebo-Controlled, Parallel-Group, Treatment-Withdrawal Study to Evaluate the Efficacy and Safety of Esomeprazole for the Treatment of Gastroesophageal Reflux Disease (GERD) in Infants Aged 1 to 11 Months, Inclusive  Open-label phase =5 to 7 days  Randomized withdrawal phase =up to 1 week	1.5, 2.5, 3, 5 and 10 mg  Stratified by weight:  3 kg≤Weight<5 kg : open-label phase: 3 mg, randomized withdrawal phase: 3 mg, 1.5 mg or placebo  5 kg≤Weight<7.5 kg : open-label phase: 5 mg, randomized withdrawal phase: 5 mg, 2.5 mg or placebo  7.5 kg≤Weight<12 kg : open-label phase: 10 mg, randomized withdrawal phase: 10 mg, 5 mg or placebo

AZ Protocol #	Age Group	Design	Dose(s)
D9614C00097	Children 1 year up to 11 years, inclusive	A Multicenter, Parallel-Group Study to Evaluate the Safety and Clinical Outcome of Once Daily Esomeprazole for the Treatment of Gastroesophageal Reflux Disease (GERD) in Pediatric Patients Ages 1-11 Years, Inclusive  Duration =8 weeks	5, 10 and 20 mg  Stratified by weight:  8 kg≤Weight<12 kg: 5 or 10 mg 12 kg≤Weight<60 kg: 10 or 20 mg

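### Inclusion criterion 2 contradicts the stated population: its full-term alternative has no upper age, and its 28 to 44 week range has no time point

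*Protocol*

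**What the plan says.** Four places in the protocol describe the population with an upper age:

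- The title: "in neonatal patients, including premature and up to 1 month corrected age".
- The synopsis paragraph on centres and patient numbers, which repeats that limit and adds a gestational age of 28 to 44 weeks.
- The synopsis, target patient population: "Male and female neonatal patients, including premature and up to 1 month corrected age, with symptoms of GERD", followed by the same range of weeks in brackets, applied to every patient.
- The list of definitions, where neonatal patients are "Infants who are born full term or premature (up to one month corrected age").

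Section 3.3.2, criterion 2, is worded differently. It begins "Patients must be full term or have gestational age" and ends the range at "44 weeks (calculated from last menstruations or ultrasound"). It does not mention corrected age. It makes full term an alternative to the range, which neither synopsis paragraph does.

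The nearest other entry limit is criterion 3, which concerns the ward: "Patients must be an inpatient in the Neonatal Intensive Care Unit (NICU), special care nursery, or equivalent hospital ward at the point of study entry". That restricts the setting, not the age. None of the other inclusion criteria and none of the 15 exclusion criteria sets an age limit.

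Section 3.3.5.3 allows no exceptions to the inclusion and exclusion criteria and requires patients enrolled in error to be discontinued. Section 4.2 lists the demographic data as date of birth, sex and race.

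**The concern.** Eligibility is decided by the numbered criteria, and criterion 2 does not carry the age limit that defines the trial. It has two separate faults.

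First, full term describes an infant at birth and says nothing about age now. Because it is joined to the range by *or*, a term-born infant qualifies without the range being consulted.

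Second, the range gives no time point. An upper bound of 44 weeks suggests age at study entry, but gestational age counted from the last menstrual period or ultrasound is also the usual description of age at birth. The criterion does not say which is meant.

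At stake is whether three centres in three countries, each expected to randomise about 30 infants, apply the same rule. It also matters whether an infant past 1 month corrected age counts as correctly enrolled. By the title that infant is outside the population. By criterion 2 that infant is inside it, so the discontinuation rule for incorrect enrolment is not triggered.

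**Working it through.** The plan gives no figure to reproduce. The check tests example infants against the criterion and against the stated population.

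**Inputs.** The range of 28 to 44 weeks and the full-term alternative come from Section 3.3.2. The limit of 1 month corrected age comes from the title, synopsis and definitions. Two conventions are assumed, because the protocol does not state them: term is 40 weeks for calculating corrected age, and birth at 37 weeks or later counts as full term.

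**Formulas.**

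- Postmenstrual age at entry = gestational age at birth + age since birth.
- Corrected age = postmenstrual age − 40 weeks.

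**Step 1: which reading of the range fits the title?** As age at entry, the upper bound is 44 − 40 = 4 weeks, or 28 days, corrected. A calendar month is 365.25 / 12 = 30.4 days, so this is about 1 month. As age at birth, the range sets no limit on current age. The entry reading is therefore the one that agrees with the title.

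**Step 2: example infants under the entry reading** (all ages in weeks).

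| Born at | Age now | Postmenstrual | Corrected | In stated population | Meets criterion 2 as written | Meets range alone |
|---|---|---|---|---|---|---|
| 28 | 16 | 44 | 4 | yes | yes | yes |
| 38 | 2 | 40 | 0 | yes | yes | yes |
| 40 | 4 | 44 | 4 | yes | yes | yes |
| 40 | 12 | 52 | 12 | no | yes | no |
| 40 | 26 | 66 | 26 | no | yes | no |

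**Step 3: what does the full-term alternative add?** Term-born infants up to 44 weeks postmenstrual age already fall within the range, as rows 2 and 3 show. Under the entry reading, the alternative therefore has only one effect: it admits term-born infants above 44 weeks (rows 4 and 5).

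**Step 4: does the birth reading remove the problem?** No. The two older term-born infants still qualify, and preterm infants lose their upper limit as well. For example, an infant born at 28 weeks and now 30 weeks old is 28 + 30 = 58 weeks postmenstrual, or 58 − 40 = 18 weeks corrected, and would pass. The conclusion does not rest on this less plausible reading; row 4 is enough.

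**The case against.** The strongest reply is that the upper age is stated repeatedly. It is in the title, twice in the synopsis, and in the definition of the term that the objectives use for the trial's patients. Criterion 2 seems to echo that definition, and an investigator who reads the whole protocol would know the limit. Criterion 3 also requires a neonatal or equivalent ward, where a 12-week-old term-born infant will be uncommon. Both points stand. They reduce the likely number of such enrolments, but they do not change what the binding sentence admits.

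A reader might also infer several stronger things that the documents do not support:

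- **That the protocol has no upper age at all.** It has one; it is missing from the numbered criteria.
- **That all infants born before 28 weeks are shut out.** That follows only if the weeks are age at birth, the reading that fits the title less well. What stands is that their status is unstated.
- **That older infants would make the result unusable for the stated population.** Section 1.1 reports daily regurgitation in 50% of infants at 0 to 3 months and 67% by 4 to 6 months. Those figures concern common infant reflux. They are not the video and cardiorespiratory count in symptomatic inpatients, and they show no change within the first 3 months. A mix of ages does not in itself bias a randomised comparison.
- **That overlap with the sponsor's study of "Infants 1 month up to 11 months, inclusive" (Appendix C) harms this trial.** That study supports 1 month as the intended boundary and shows nothing more.

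**Conclusion.** The point holds as an internal contradiction. Criterion 2 does not carry the limit of 1 month corrected age found in the title, synopsis and definitions. Under either reading of the weeks it admits a term-born infant well past that limit, such as one born at 40 weeks and now 12 weeks old. Because Section 3.3.5.3 gives the numbered criteria the final word, the passages need to be reconciled.

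The size in patients is unknown. The documents give no age distribution, and the ward requirement should keep the number small among the planned minimum of 90. No bias in the treatment comparison is claimed. The example ages assume term at 40 weeks, but the fault in the wording does not depend on that assumption. This is worth correcting for clarity and uniform enrolment; it does not threaten the design.

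**What to change.** Bring criterion 2 into line with the title, both synopsis paragraphs and the definition of neonatal patients:

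1. Delete *full term or*, or attach the limit of 1 month corrected age to it.
2. State that the range is postmenstrual age (gestational age at birth plus age since birth) on the day of randomisation.
3. Give the upper bound in weeks and days so that it matches 1 month corrected age. With term at 40 weeks this is 44 weeks 0 days. A bound of 44 completed weeks should be avoided, because it can run to 44 weeks 6 days, which is 4 × 7 + 6 = 34 days corrected.
4. Have the sponsor confirm whether infants born before 28 weeks but in range at entry are eligible. An infant born at 25 weeks and now 11 weeks old is 36 weeks postmenstrual: in range at entry, but out of range if the weeks are age at birth. Step 2 would make such infants eligible, so this should be a deliberate decision.
5. Record gestational age at birth alongside date of birth. It is not among the demographic items listed in Section 4.2, and corrected age cannot be derived from those items alone.

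The cost is one reworded criterion, matching text in the synopsis, and one eCRF field. The downside is that a few older term-born infants admitted by the current wording become ineligible; the title already places them outside the trial.
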